12 OCT 2020

## 5. SELECTION AND WITHDRAWAL OF PATIENTS

### 5.1. Patient Inclusion Criteria

A patient must meet all of the following inclusion criteria to be eligible to be randomized in the clinical study:

#### *Population*

1. Male and female patients, at least 40 years of age at Screening
2. Not eligible for oral pirfenidone and nintedanib due to national formulary restrictions OR intolerant to or unwilling to start oral pirfenidone and nintedanib, if previously offered

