## 5.3. Study Restrictions

Patients are not to receive pirfenidone or nintedanib within 3 days prior to randomization to the study and during participation in Part A of the study. Nintedanib, but not oral pirfenidone, use is allowed if deemed necessary by the investigator during Part B of the study. In the event of an acute exacerbation, any treatment deemed necessary by the investigator is acceptable until the resolution of the event. Other than brief periods of medically appropriate treatment for acute IPF exacerbation, patients will not receive any other therapy for the treatment of IPF during Part A. If in the opinion of the investigator, a patient is in need of treatment with oral pirfenidone or nintedanib during Part A, the patient should be discontinued from the study and return to the clinic for their Early Termination visit. Oxygen use is allowed during the study.

Avalyn Pharma, Inc.  
AP01-002

Protocol v2.1  

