#### **6.2.1. Visit 1 – Screening (Day -30 to Day -1)**

- Informed Consent
- Demography
- Medical history and concomitant medications including past 3 months
- Complete physical exam (PE) and vital signs, including height and weight
- Standard 12-lead ECG
- Saturated Oxygen (SaO2)
- Spirometry and DLCO
- Blood samples for laboratory tests (Chemistry including AST and ALT, Hematology)
- Urinalysis
- Urinary pregnancy test for females of childbearing potential (FOCBP) only
- Confirmation of IPF diagnosis as described in Section 5
- Inclusion/Exclusion Review

Leicester Cough Monitor (LCM) training. Patients that pass all of the screening criteria and are deemed eligible for the study will be provided with a LCM between the Screening and Baseline visit to wear for 24 hours. Patients will bring the LCM with them to the site at the Baseline visit. Optionally, patients may return to the clinic one day prior to the Baseline visit to receive their LCM and perform the 24-hour Baseline LCM reading; returning the LCM to the clinic the following day.

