## **8.9. Treatment of Patients**

### **8.9.1. Concomitant Medications and/or Treatments**

Patients are prohibited from receiving pirfenidone or nintedanib within 3 days prior to randomization to the study and during participation in Part A of the study. Other than brief periods of medically appropriate treatment for acute IPF exacerbation, patients will not receive any other therapy for the treatment of IPF in Part A of the study. If in the opinion of the investigator, a patient is in need of treatment with oral pirfenidone or nintedanib during Part A, the patient should be discontinued from the study and return to the clinic for their Early Termination visit. Nintedanib, but not oral pirfenidone, use is allowed if deemed necessary by the investigator during Part B of the study. If AP01 is stopped during treatment of an exacerbation due to a patient's intolerance, it should be restarted when the patient has improved, however the first dose should be observed for tolerance. Oxygen use is allowed during the study.

Due to the low systemic levels expected with delivery by inhalation, drug-drug interactions are unlikely and unexpected.

Patients who are experience excessive coughing during study drug administration will be required to inhale 1 - 2 puffs (90 - 100 µg) of salbutamol within 10 minutes prior to subsequent study drug dosing. Pre-treatment with salbutamol will be documented on the Concomitant Medications eCRF page.

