12 OCT2020

## **9 RANDOMIZATION AND BLINDING PROCEDURES**

### **9.1 Randomization**

Patients will be randomized in a 1:1 ratio to receive AP01 either 50 mg once daily or 100 mg twice daily; both regimens being administered by the eFlow. The randomization schema will be stratified by region (Asia-Pacific and Europe) and by disease severity (FVC < 50% predicted and FVC ≥ 50% predicted). The first 20 patients randomized in the study must have FVC ≥ 50% predicted at Screening. After the first 20 patients have been randomized, patients with FVC 40% < 50% predicted will be allowed to be randomized in the study but randomization for these patients will be capped at 20.

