The primary endpoint of interest for efficacy is the absolute change from Baseline to Week 24 in FVC % predicted. Linear mixed-effects models will be used to estimate slopes representing the mean change from Baseline to Week 24 in each treatment group, and the difference between treatment groups will be examined. Baseline FVC % predicted, region, age at screening, sex, baseline D_{LCO} % predicted, and baseline progression-related biomarker (CXCL13, CCL18, MMP3) values each categorized as >Median level vs. ≤Median level will be included as covariates in the model. Similar modeling strategies will be employed for longer-term data obtained from Part B of the study.

No control group is included in this study; however, there is ample data in the literature showing a consistent rate of decline in IPF patients not receiving anti-fibrotic therapies. Historical data from the placebo groups of the three Phase III clinical trials of oral pirfenidone (ASCEND and CAPACITY trials) showed an average decline in FVC % predicted of ~4% at 6 months. These results will be used as a historical comparator. For each AP01 treatment group, a one sample Wald test will test H_0 : mean change from Baseline to Week 24 in FVC % predicted $\leq -4\%$ vs H_1 : mean change from Baseline to Week 24 in FVC % predicted $> -4\%$. For each AP01 treatment group, a 95% one-sided confidence interval will be derived for the difference (between A01 and historical reference) in the mean change from Baseline to Week 24 in FVC % predicted. Additionally, we will compare the change from baseline in FVC % predicted at Week 24 for each treatment group to the average decline in FVC % predicted at 24 weeks for patients with no documented antifibrotic treatment calculated from a set of (1) Pulmonary Fibrosis Foundation (PFF) Registry patients and (2) Australian IPF Registry patients, with matching baseline characteristics. For each treatment group and each registry, a two-sided Wald test will test: H_0 : 24-week $FVC\ decline_{AP01\ group} = 24\text{-week}\ FVC\ decline_{registry}$ vs. H_1 : 24-week $FVC\ decline_{AP01\ group} \neq 24\text{-week}\ FVC\ decline_{registry}$. For each of the 2 AP01 treatment groups and for each of the 2 registries, a 95% two-sided confidence interval will be derived for the difference (between AP01 and registry) in the mean change from Baseline to Week 24 in FVC % predicted.

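### The external comparisons may set a partly pretreated trial population against patients with no documented antifibrotic use, and prior use is listed but neither summarised nor used in any analysis

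*Protocol*

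**What the plan says.** Criterion 2 (Protocol section 5.1) has three routes: not eligible for the oral drugs under national formulary rules, intolerant, or unwilling to start. The last two are worded "intolerant to or unwilling to start oral pirfenidone and nintedanib, if previously offered". Section 5.3 sets the washout: "Patients are not to receive pirfenidone or nintedanib within 3 days prior to randomization". Section 8.9.1 repeats it: "Patients are prohibited from receiving pirfenidone or nintedanib within 3 days prior to randomization".

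SAP section 8 has no concurrent control and uses two kinds of external comparator:

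- The first is "Historical data from the placebo groups of the three Phase III clinical trials of oral pirfenidone", reduced to a constant of -4% at 6 months and tested one-sided for each arm.
- The second is the average 24-week decline "for patients with no documented antifibrotic treatment calculated from a set of" patients in two registries, matched on baseline characteristics that are not named and tested two-sided for each arm and registry.

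Randomisation uses two factors (Protocol section 9.1): "The randomization schema will be stratified by region (Asia-Pacific and Europe) and by disease severity". The model covariates (SAP section 8.1) are baseline FVC, region, age, sex, DLCO and three biomarkers. The subgroups (SAP section 6.6) are the same variables plus oxygen use. The baseline tables (SAP sections 7.2 and 7.4) do not include prior antifibrotic use. Under SAP section 7.6 a drug stopped before the first dose is a prior medication. Prior medications are listed per patient; only concomitant ones are tabulated. The Screening visit (Protocol section 6.2.1) collects "Medical history and concomitant medications including past 3 months".

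**The concern.** A patient who enters through the intolerance route has taken an antifibrotic and may have stopped it only days before the baseline FVC. The Protocol introduction says the oral drug slows progression. A patient who has recently left it, or who is selected for not tolerating it, may have a different 24-week course from one who never took it. If such patients make up a material part of an arm, the difference from the external reference contains that population difference as well as any effect of AP01.

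The trial has no untreated arm, so these comparisons are its only evidence against no treatment, and the SAP attaches Wald tests and confidence intervals to them. As the outputs are planned, the tables would not show what share of either arm was previously treated.

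**Working it through.** **Inputs from the documents.** The SD is 4.5 and n is 50 per arm (Protocol section 11.1, SAP section 3.5). The stated two-sided 95% half-width is 1.25. The cited Phase 3 trial of oral pirfenidone showed mean Week 26 changes of -1.5 (active) and -3.9 (placebo), a gap of 3.9 - 1.5 = 2.4 points. The test against -4% is paired with a one-sided 95% interval, so one-sided alpha is taken as 0.05.

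**The plan's own figure.** SE = 4.5/√50 = 0.636, and 1.96 × 0.636 = 1.247. This reproduces 1.25.

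**Assumed inputs.** The documents do not give the share p of previously treated patients, or the difference d between their 24-week change and that of never-treated patients. I take p from 10% to 50% and d from 0.5 to 2.4 points in either direction.

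**Shift in the arm mean = p × d.** The false-positive rate against -4% is Φ(shift/SE - 1.645). For the registry test, with the registry mean treated as fixed, it is Φ(shift/SE - 1.96) + Φ(-shift/SE - 1.96).

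| p | d | Shift | Share of 1.25 | One-sided, prior users decline less | One-sided, prior users decline more | Two-sided registry |
|---|---|---|---|---|---|---|
| 10% | 0.5 | 0.05 | 4% | 0.059 | 0.042 | 0.051 |
| 30% | 1.2 | 0.36 | 29% | 0.140 | 0.014 | 0.087 |
| 50% | 2.4 | 1.20 | 96% | 0.595 | <0.001 | 0.470 |

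Middle row: 0.30 × 1.2 = 0.36 and 0.36/0.636 = 0.566. Then Φ(0.566 - 1.645) = 0.140 and Φ(-0.566 - 1.645) = 0.014.

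**Between the randomised arms** the expected shift is zero. The SD of the chance difference in share is √(p(1-p) × 2/50): 0.06 at 10%, 0.092 at 30% and 0.10 at 50%. At 30% and d = 1.2 that moves the between-arm difference by about 0.092 × 1.2 = 0.11 points (one SD).

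**Residual drug.** The Protocol gives a pirfenidone half-life of about 2.4 hours (section 1.2.2), so 3 days is 72/2.4 = 30 half-lives. The documents give no half-life for nintedanib.

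**The case against.** Several stronger readings are tempting, and the documents do not support them.

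- *The plan ignores prior use.* It does not: SAP section 7.6 lists prior medications for every patient. What is missing is a summary and any analytic use.
- *Older exposure cannot be recovered.* The 3-month wording at Screening can be read as a minimum. Medical history has no stated look-back, and checking criterion 2 should leave source evidence of how each patient qualified.
- *Prior use should have been stratified or put in the primary model.* That model contains only AP01 patients. Neither step would by itself align an arm with an outside constant or registry.
- *The comparators are never-treated patients.* SAP section 8 describes the placebo reference in terms of patients not receiving antifibrotics, which is concurrent status. The placebo patients' history before those trials is not given, and the registry exclusion is not said to be lifetime. AP01 patients are also kept off both oral drugs in Part A, apart from any treatment judged necessary for an acute exacerbation.
- *The error is about as large as the whole half-width.* That needs p = 50% and d = 2.4 together. No document supports that share, and 2.4 is an on-drug versus placebo gap, not a measured effect of stopping or of intolerance.
- *The washout leaves drug on board.* For pirfenidone this is unlikely.

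The Protocol also calls the external comparisons exploratory (section 11.5.1), and the primary objective is safety. All of this stands and narrows the point. It leaves in place that the intolerance route can admit prior users and that the planned tables and analyses would neither show nor examine them.

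**Conclusion.** The point holds in limited form. The external comparisons may mix previously treated and untreated patients, and the planned tables and analyses do not allow the extent to be judged. An assumed 30% of prior users differing by 1.2 points shifts an arm mean by 0.36 points. If prior users decline less, the one-sided error rate against -4% rises from 0.05 to about 0.14; if they decline more, it falls to about 0.01. Both the share and the difference are assumptions, and the direction cannot be settled from the documents.

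Only the intolerance route implies earlier exposure; patients unwilling to start are by that wording not prior users. The effect is confined to the exploratory external comparisons. A reader might infer that the randomised dose comparison is biased, but it is exposed only to chance imbalance. This is an improvement the plan should make, not a flaw that invalidates it.

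**What to change.** 1. Retrieve from source which route of criterion 2 each patient met, and any prior use of oral pirfenidone or nintedanib with the last dose date.
2. Add never/ever prior antifibrotic use, by arm, to the baseline table in SAP section 7.4.
3. State in SAP section 8 whether the registry exclusion is lifetime or covers only the 24 weeks.
4. Repeat the -4% and registry comparisons in antifibrotic-naive patients, shown beside the full set as a sensitivity analysis. Label it as added after the preliminary 6-month data were reviewed: the Protocol records the DSMB review on 12 October 2020, and SAP version 3.0 is dated 15 July 2021.

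No change to stratification, the primary-model covariates or the washout is needed, and no rule that an effect may be claimed only if the two sets agree.

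The cost is one retrospective query, one table row and one repeat of existing comparisons. Intervals widen in the naive subset. If 30% of an arm were prior users, 35 patients would remain and the half-width would be 1.96 × 4.5/√35 = 1.49 instead of 1.25. If prior users prove few, the table row largely settles the question.

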#### *Diagnosis of IPF*

3. Clinical symptoms consistent with IPF of  $\geq 12$  months duration (with or without IPF diagnosis)
4. Diagnosis of IPF, defined as the first instance in which a patient was informed of having IPF, no more than 60 months before randomization.
  - Patients that have had an IPF diagnosis  $\geq 1$  year, the following criteria must be met:
    - HRCT and/or Surgical Lung Biopsy findings consistent with UIP. If honeycombing is not present on the HRCT, then one or both of the following criteria must be present:
      - Disease progression since diagnosis by HRCT and/or
      - An absolute loss of FVC  $\geq 5\%$  percent predicted over the past 12 months
  - Patients that have had IPF diagnosis within the last year, the following criteria must be met:
    - Diagnosis of Usual Interstitial Pneumonia (UIP) or IPF by HRCT (HRCT must be performed within 12 months prior to Screening) and/or Surgical Lung Biopsy as outlined in Table 4:

Avalyn Pharma, Inc.  
AP01-002

Protocol v2.1  
12 OCT 2020

**Table 4: Diagnosis of UIP or IPF by HRCT and Surgical Lung Biopsy**

CT pattern as determined by Fleischner Society White Paper 	Surgical Lung Biopsy Not Available	Pathology Panel: Definite UIP	Pathology Panel: Probable UIP	Pathology Panel: Possible UIP	Pathology Panel: Inconsistent with UIP or Not Classifiable
Typical UIP Pattern	Eligible	Eligible	Eligible	Eligible	NOT Eligible
Probable UIP Pattern	Eligible	Eligible	Eligible	Eligible	NOT Eligible
Indeterminate or most consistent with non-IPF diagnosis	NOT Eligible	NOT Eligible	NOT Eligible	NOT Eligible	NOT Eligible

5. Extent of fibrotic changes (honeycombing, reticular changes) greater than the extent of emphysema on HRCT scan
6. No features supporting an alternative diagnosis on transbronchial biopsy, BAL, or surgical lung biopsy, if performed

*IPF Disease Severity and Progression*

7.  $40\% \leq \text{FVC} \leq 90\%$  predicted at Screening based on Global Lung Initiative equations. The first 20 patients randomized must have  $\text{FVC} \geq 50\%$  predicted. After the first 20 patients have randomized, patients with  $\text{FVC} 40\% < 50\%$  predicted will be allowed to be randomized in the study but randomization for these patients will be capped at 20
8. Change in FVC (measured in liters) between Screening and Day 1 (pre-dose measurement) must be a  $< 10\%$  relative difference, calculated as:

$$\frac{\text{Screening FVC (L)} - \text{Day 1 FVC (L)}}{\text{Screening FVC (L)}} \times 100\%$$

9.  $30 \leq \% \text{DLCO} \leq 90\%$  at Screening
10. In the investigator's opinion, no evidence of improvement in measure of IPF disease severity over the preceding year
11.  $\text{FEV}_1/\text{FVC} \geq 70\%$

*Informed Consent and Protocol Adherence*

12. Able to understand and sign a written informed consent form
13. Able to understand the importance of adherence to study treatment and the study protocol and willing to follow all study requirements, including the concomitant medication restrictions, throughout the study

Avalyn Pharma, Inc.  
AP01-002

Protocol v2.1  
12 OCT 2020

## 5.2. Patient Exclusion Criteria

The presence of any of the following exclusion criteria excludes a patient from study enrollment:

### *Disease-Related Exclusions*

1. Significant clinical worsening of IPF between Screening and Day 1, in the opinion of the investigator
2. Not a suitable candidate for enrollment or unlikely to comply with the requirements of this study, in the opinion of the investigator
3. History of acute IPF exacerbation requiring hospitalization in the last 3 months
4. History of clinically significant environmental exposure known to cause pulmonary fibrosis, including but not limited to drugs (such as amiodarone), asbestos, beryllium, radiation, and domestic birds
5. Known explanation for interstitial lung disease, including but not limited to radiation, drug toxicity, sarcoidosis, hypersensitivity pneumonitis, bronchiolitis obliterans organizing pneumonia, human immunodeficiency virus, viral hepatitis, and cancer
6. Clinical diagnosis of any connective tissue disease, including but not limited to scleroderma, polymyositis/dermatomyositis, systemic lupus erythematosus, and rheumatoid arthritis
7. Current diagnosis of asthma or chronic obstructive pulmonary disease
8. Clinical evidence of active infection, including but not limited to bronchitis, pneumonia, sinusitis, urinary tract infection, or cellulitis

### *Medical Exclusions*

9. Females with a positive pregnancy test at Screening or are currently breastfeeding
10. Any history of malignancy likely to result in significant disability or likely to require significant medical or surgical intervention within the next 6 months. This does not include minor surgical procedures for localized cancer (e.g., basal cell carcinoma)
11. Any condition other than IPF that, in the opinion of the investigator, is likely to result in the death of the patient within the next 6 months
12. History of severe hepatic impairment or end-stage liver disease or ALT or AST greater than 5 times the upper limit of normal at Screening
13. History of end-stage renal disease requiring dialysis
14. Participation in a clinical study with administration of an investigational drug product within the previous 30 days, or five half-lives of the previously administered investigational product

## 5.3. Study Restrictions

Patients are not to receive pirfenidone or nintedanib within 3 days prior to randomization to the study and during participation in Part A of the study. Nintedanib, but not oral pirfenidone, use is allowed if deemed necessary by the investigator during Part B of the study. In the event of an acute exacerbation, any treatment deemed necessary by the investigator is acceptable until the resolution of the event. Other than brief periods of medically appropriate treatment for acute IPF exacerbation, patients will not receive any other therapy for the treatment of IPF during Part A. If in the opinion of the investigator, a patient is in need of treatment with oral pirfenidone or nintedanib during Part A, the patient should be discontinued from the study and return to the clinic for their Early Termination visit. Oxygen use is allowed during the study.

Avalyn Pharma, Inc.  
AP01-002

Protocol v2.1  
12 OCT 2020

#### **5.4. Screening Rules and Rescreening**

Patients who do not meet all the inclusion criteria or who meet at least one of the exclusion criteria will be considered screen failures. Patients may be rescreened after failing screening in the event of changes in responses to the eligibility criteria.

#### **5.5. Randomization Criteria**

Randomization will occur at Baseline/Study Visit 2. Patients must continue to meet all of the inclusion and none of the exclusion criteria to be randomized.

#### **5.6. Patient Withdrawal Criteria**

Patient participation in the study is purely voluntary; patients can withdraw consent at any time for any reason without effect on subsequent care. This is an open-label study in which the investigator is aware of the patient's treatment assignment. The investigator, in consultation with the Medical Monitor, or the Medical Monitor may exercise his or her medical judgment to terminate a patient's participation in the study due to clinically significant changes in any clinical or laboratory parameter. If in the opinion of the investigator, the patient is failing the study drug for lack of efficacy, as evidenced by an excessive decline of FVC, during Part A of the study, the patient can be withdrawn and placed on alternative therapies. During Part B of the study, the investigator may choose to add nintedanib, but not oral pirfenidone, to the patient's treatment regimen.

Any randomized patient desiring to discontinue prior to study completion should be encouraged to discuss his or her reasons and concerns with the investigator. If, after discussion, the patient still chooses to discontinue participation in the study, the patient should be encouraged to attend an Early Termination visit. (Patients that discontinue during the screening process will be considered screen failures.) Patients who are discontinued during a scheduled visit will be encouraged to complete all unique assessments for both that study visit and the End of Treatment visit at the time of discontinuation. If a patient is still participating in Part A and has had a HRCT scan within the past month, the HRCT from the End of Treatment visit will not be performed.

An End of Study case report form (CRF) page will be completed for every patient who receives study medication whether or not the patient completes the study. The reason for any early discontinuation from the study will be indicated on this form. The primary reason for any early termination will be selected from the following standard categories:

- Adverse Event: Clinical or laboratory events occurred that in the medical judgment of the investigator, in consultation with the Medical Monitor and Avalyn Pharma, represents an unacceptable risk to the patient if he/she continues in the study. This includes serious and non-serious AEs regardless of relationship to study medication. The investigator must follow the patient until the AE resolves or satisfactorily stabilizes
- Withdrawal of Consent: The patient desires to withdraw from further participation in the study in the absence of a medical need to withdraw determined by the investigator. If the patient gives a reason for this desire, this will be recorded on the CRF
- Pregnancy
- Lack of tolerability to drug or device
- Lost to Follow-up: The patient fails to complete the study and site personnel are unable to contact the patient within 30 days post-dose
- Death

Avalyn Pharma, Inc.  
AP01-002

Protocol v2.1  

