### **8.9.2. Treatment Compliance**

Administration of the first dose of IP will be observed by the investigator or designee; time of administration and confirmation of full dose being administered will be noted in the eCRF. Patients will bring all unused ampoules to each visit for drug accountability and compliance assessment. At the discretion of the investigator, patients that are not in compliance with study dosing and procedures will be discontinued from the study.

Avalyn Pharma, Inc.  
AP01-002

Protocol V2.1  

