6.6. Subgroups

Subgroup analyses will be performed based on baseline groupings for FVC % predicted (FVC % predicted \leq 65, 65 < FVC % predicted < 80, and FVC % predicted \geq 80 at Baseline), region (Asia-Pacific and Europe), supplemental oxygen use (Y/N), age at screening categorized as >Median level vs. \leq Median level, sex, DLCO % predicted categorized as >Median level vs. \leq Median level, and progression-related biomarkers (CXCL13, CCL18, MMP3) each categorized as >Median level vs. \leq Median level provided each stratum contains at least 10 patients. Analyses of the primary efficacy endpoint will be performed by each subgroup in addition to by treatment group. In addition, a general

This document is confidential.

SAP Version: 3.0 (15JUL2021)
Controlled Document ID: **3903A.01**, Effective Date 29-Oct-2018
Filing requirements: TMF

Page 24 of 52

Statistical Analysis PlanSponsor: Avalyn Pharma, Inc.; Protocol No.: AP01-002

safety summary (overall AE summary, summary of respiratory [SOC respiratory, thoracic and mediastinal disorders] TEAEs by Preferred Term and summary of tolerability including cough due to drug administration and bronchospasm after in-clinic drug administration) will be performed by each subgroup in addition to by treatment group.

This document is confidential.

SAP Version: 3.0 (15JUL2021)
Controlled Document ID: **3903A.01**, Effective Date 29-Oct-2018
Filing requirements: TMF

Page 25 of 52

Statistical Analysis PlanSponsor: Avalyn Pharma, Inc.; Protocol No.: AP01-002

7. Demographic, Other Baseline Characteristics and Medication**7.1. Patient Disposition and Withdrawals**

The number of patients in each study population will be summarized by treatment group and overall. In addition, for each study part (Part A and Part B), patients' status with regard to study treatment and follow-up will also be summarized by treatment group and overall, along with the reasons for study discontinuations. The timing of the switch to 100 mg twice daily in Part B for 50 mg once daily patients and duration of time on 100 mg twice daily will be summarized.

All patient disposition data will be presented in a listing.

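### The closed list of six termination reasons in Protocol 5.6 has no place for lack of efficacy, need for antifibrotic therapy or non-compliance, so the by-arm disposition table cannot show these exits

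*Protocol*

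**What the plan says.** Protocol 5.6 requires an End of Study form for every patient who receives study drug and fixes how the exit reason is recorded: "The primary reason for any early termination will be selected from the following standard categories". The list that follows has six entries: adverse event, withdrawal of consent, pregnancy, "Lack of tolerability to drug or device", lost to follow-up, and death. There is no 'Other'.

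The protocol describes three further ways in which a patient may leave:

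- **Lack of efficacy, Part A (Protocol 5.6, the section that holds the list).** A patient may be withdrawn and given other therapy if, in the investigator's opinion, "the patient is failing the study drug for lack of efficacy, as evidenced by an excessive decline of FVC".
- **Need for oral pirfenidone or nintedanib, Part A (Protocol 4.1, 5.3 and 8.9.1; repeated in SAP 3.3).** If the investigator sees such a need, "the patient should be discontinued from the study and return to the clinic for their Early Termination visit".
- **Non-compliance, either part (Protocol 8.9.2).** At the investigator's discretion, "patients that are not in compliance with study dosing and procedures will be discontinued from the study".

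SAP 7.1 summarises patient status for each study part, by treatment group and overall, "along with the reasons for study discontinuations". It adds no categories of its own.

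**The concern.** A form that offers only these six reasons leaves a site with no correct entry for a patient removed because FVC fell too fast, because an antifibrotic was needed, or because the drug was not being taken. Different sites may well code the same exit differently.

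The exits that lack a code include those that say most about efficacy. Protocol section 2 makes comparison of the two regimens' safety and efficacy an objective, meant to guide dosing in later studies. The study is open-label, so an investigator who judges that a patient is failing knows the dose, and removals on that ground may differ between arms. A reader would look for this in the disposition table, and the list as written has no row for it.

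There is also a consequence for missing data. The sensitivity analyses in SAP 8.1 treat all early terminations other than deaths alike: later visits receive the average change of same-cohort patients who have data at that visit. A patient taken out for excessive decline is thereby given the course of those who stayed. Without a recorded reason, no pre-specified analysis can single these patients out.

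**Working it through.** The plan states no figure to reproduce. The check sets removal routes against codes, tests whether the existing codes could absorb the unmatched routes, and traces where the reason is used.

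**Step 1. Routes against categories.**

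| Removal route | Source | Matching category |
|---|---|---|
| Patient's own wish | Protocol 5.6 | Withdrawal of consent |
| Important change in a clinical or laboratory measure | Protocol 5.6 | Adverse event, if its risk test is met |
| Symptoms persisting despite beta-2-agonist | Protocol 8.6 | Lack of tolerability |
| Pregnancy | Protocol 10.1.5.5 | Pregnancy |
| Lack of efficacy / FVC decline, Part A | Protocol 5.6 | None |
| Need for oral pirfenidone or nintedanib, Part A | Protocol 4.1, 5.3, 8.9.1 | None |
| Non-compliance, either part | Protocol 8.9.2 | None |

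Four routes have a category and three do not.

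**Step 2. Could an existing category absorb the three?**

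- *Adverse event* requires an event that "represents an unacceptable risk to the patient if he/she continues in the study". Protocol 10.1.1.1 records worsening of a pre-existing condition as an AE, so some FVC declines qualify. A patient who is merely not benefiting, or not taking the drug, does not.
- *Withdrawal of consent* is limited to the patient's own wish "in the absence of a medical need to withdraw determined by the investigator". That excludes a need for other therapy that the investigator has determined.
- *Lack of tolerability* concerns drug or device. It does not describe inefficacy or non-compliance, but a site forced to choose could use it.
- *Pregnancy*, *lost to follow-up* and *death* do not apply.

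**Step 3. Where the reason is used.**

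- SAP 7.1 tabulates it by arm.
- SAP 8.1 separates only deaths from other early terminations in the imputation, so a finer code would alter no FVC analysis now planned.
- The *Non-compliance* heading in SAP 5.4 is a protocol-deviation category, not an exit reason.

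**Step 4. Size.** The input is 50 patients per arm (Protocol synopsis, Number of Patients). With k misfiled exits in an arm, that arm's rate for the receiving reason rises by 100 × k/50 = 2k percentage points.

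- k = 1: 100 × 1/50 = 2 points
- k = 2: 100 × 2/50 = 4 points
- k = 5: 100 × 5/50 = 10 points

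The documents give no expected k, so these values are assumptions that only show the scale. If k were 5 in one arm and 2 in the other, with all filed under the same reason, the apparent difference between arms would be 10 − 4 = 6 points.

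**The case against.** The strongest reply is that the gap matters less than it seems. Four parts of it deserve an answer.

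**No misfiling is documented.** A reader might infer that these exits are in fact recorded as adverse events or withdrawn consent. The documents do not show this. The eCRF is not among them and may offer more options, a site might leave the field blank, and the consent category is excluded by its own definition for a need determined by the investigator. For some FVC declines the adverse event category would be correct. This stands: misfiling follows from the rule as written but has not been observed.

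**No primary safety result is shown to be affected.** A reader might infer that AE-related discontinuation is a primary tolerability result and would be inflated. The synopsis lists the primary measures as treatment-emergent AE rates, spirometry after the first dose, deaths, laboratory findings and vital signs; discontinuation is not one of them. The tables of AEs leading to termination (SAP 10.1) are by organ class, preferred term and grade, which points to AE records, where Protocol 10.1.4.3.1 captures the action taken. Nothing says they are built from the End of Study code. This also stands.

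**The exits are not invisible.** Antifibrotic starts are collected as concomitant medication until 30 days after the last dose (SAP 7.6), in-clinic FVC is listed (SAP 8.1), and compliance and deviations are summarised by arm (SAP 7.5 and 5.4). This stands in part. The exits could be reconstructed patient by patient, but the table meant to report them cannot do so.

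**The FVC estimate does not depend on the code.** This is correct. The optimism of the imputation comes from the imputation rule, not from the code list. The code is what would allow a different rule for these patients.

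Two routes are also softer than a short reading suggests: removal for FVC decline is permitted rather than required, and removal for non-compliance is discretionary.

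**Conclusion.** The point holds as a mismatch between a closed code list and the protocol's own grounds for removal. Three of the removal routes have no category, and two of these, lack of efficacy and need for an antifibrotic, bear directly on the FVC comparison. If the eCRF has no further options, a site that follows 5.6 must enter a reason that does not fit, often adverse event or lack of tolerability, and the by-arm reasons in SAP 7.1 cannot show efficacy failures. Each such exit shifts an arm's rate by 2 percentage points at 50 per arm; the number of exits, and hence the total effect, cannot be derived from the documents.

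The conclusion goes no further than disposition reporting and the loss of a reason-specific sensitivity analysis. The documents do not support a claim that a listed primary safety measure is distorted, that the dropout cannot be studied at all, or that the planned FVC estimate would differ with a better list. The point is still worth correcting because the stated rule gives a wrong entry and the remedy is cheap.

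**What to change.** 1. **Protocol 5.6 and End of Study CRF.** Add *Lack of efficacy / FVC decline*, *Need for oral pirfenidone or nintedanib*, *Non-compliance* and *Other / investigator or sponsor decision (specify)*. If the eCRF already has them, align 5.6 with it. No withdrawal criterion changes.
2. **Existing terminations.** Re-code from source notes and antifibrotic start dates under a written rule, applied without sight of treatment arm. This matters because the study is open-label and, according to Protocol 1.2.4, preliminary six-month results have already been used to choose a regimen. Extracts with the dose removed would serve.
3. **SAP 7.1.** Show the new rows by arm and study part.
4. **SAP 8.1.** Add one sensitivity analysis in which lack-of-efficacy and antifibrotic-need exits are not imputed with the average change of same-cohort patients who still have data, but under a less favourable assumption, such as continuing the patient's own observed FVC decline. State in advance what is done when a patient has too few values to estimate that decline.

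The cost is a code-list update, limited re-coding with some residual risk of bias because site staff know the dose, and one extra analysis. No new visits or measurements are needed, and the primary FVC estimate is unaffected.
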